5 SAMPLE SIZE AND POWER

Approximately 500 subjects with type 1 diabetes will participate in this trial. The sample size estimation is based on primary objective - to demonstrate that immunogenicity as assessed by TEAR rate with MYL-1601D is equivalent to that of NovoLog® during 24-week treatment. The 80% power will be achieved with 250 subjects per treatment arm to demonstrate that 90% confidence interval of treatment difference (MYL-1601D minus NovoLog®) is within prespecified \pm margin (Table 2 of the SAP) (Chow SC et al, 2002; Chow S-C et al 2003). The pre-specified equivalent margin is dependent on the final rate of NovoLog® TEAR rate. No replacement of subject will be performed if subject discontinued prematurely from the study.

Table 2: Margins and 95% CIs with different reference TEAR event rates in 500 subjects

Event Rate for Reference Product	Estimated 95% CI for the Event Rate (n=250)	Margin	Type I error 2 one-sided alpha	Power	Total N
5%	(2%,8%)	5.7%	0.05	80%	500
10%	(6%,14%)	7.9%	0.05	80%	500
15%	(11%,19%)	9.3%	0.05	80%	500
20%	(15%,25%)	10.5%	0.05	80%	500
25%	(20%,30%)	11.3%	0.05	80%	500
30%	(24%,36%)	12.0%	0.05	80%	500
35%	(29%,41%)	12.5%	0.05	80%	500
40%	(34%,46%)	12.8%	0.05	80%	500
45%	(39%,51%)	13.0%	0.05	80%	500
50%	(44%,56%)	13.1%	0.05	80%	500
55%	(49%,61%)	13.0%	0.05	80%	500
60%	(54%,66%)	12.8%	0.05	80%	500

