8.7.1 Analysis methods

Definition of Primary Endpoints

The TEAR rate during 24-week treatment period is the primary endpoint for this study. TEAR is defined as either one of the following:

- 1) Subjects who are ADA negative at baseline and become positive at any timepoint post baseline.
- 2) Subjects who are ADA positive at baseline and demonstrate 4-fold increase in titer values at any timepoint post baseline visit.

Although differences in TEAR rate is the primary endpoint for the study from a statistical perspective, given that immunogenicity is not a standard endpoint in clinical trials, this difference, even if significant, will not be assessed in isolation but will be part of totality of evidence including changes in HbA1c, FBG, insulin dose, neutralizing antibodies and injection site reactions to ensure that changes in TEAR rate, if any, are clinically correlated and meaningful.

Statistical Methodology for Primary Endpoint

The 90% confidence interval of the treatment difference (MYL-1601D minus NovoLog®) in the TEAR rate will be established using the Wald confidence limit method with multiple imputation (Section 8.7.2.1). The MYL-1601D TEAR rate will be declared equivalent to that of NovoLog® during the 24-week treatment period if the 90% confidence interval of the treatment difference in TEAR rate is within the pre-specified margin as displayed in Table 2 of the study SAP, as suggested by Chow et al. (2002; 2003). For specific reference drug rate-based margin calculation, please refer to the SAS example code in Section 10 (Appendices – SAS Example Codes).

The primary analysis will be based on the ITT population. In addition, all post-discontinuation and rescue data will be included in the analysis.

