8.7.2.1 Primary efficacy analysis

The primary efficacy analysis will be a test of equivalence for the MYL-1601D and NovoLog® groups in the TEAR rate at Week 24. The null hypothesis is non-equivalence, expressed by

$$H_0: |p_M - p_N| \geq \delta, \delta > 0$$

where p_M and p_N are the (true) proportions of subjects with TEAR in the MYL-1601D and NovoLog[®] groups, respectively, and δ is the equivalence margin. The null will be rejected in favor of equivalence if the 90% confidence interval of the treatment difference is within the range $(-\delta, \delta)$. The confidence interval as defined by Chow and Shao (2002) is constructed as

$$CI_{2\alpha} = [\hat{p}_M - \hat{p}_N - t_\alpha \hat{\sigma}, \hat{p}_M - \hat{p}_N + t_\alpha \hat{\sigma}]$$

where \hat{p}_j is the estimate of the TEAR rate p_j in each treatment group, $j \in \{M, N\}$, $\hat{\sigma}$ is the sample estimate of the standard error of the mean, and t_α the 0.05 quantile of the t distribution with $(N - 2)$ degrees of freedom with N being the pooled number of subjects in the analysis. That is, H_0 will be rejected if neither $-\delta$ nor δ is contained within the 90% confidence interval.

To minimize any bias due to missing data, the primary efficacy analysis will use multiple imputation to fill in missing ADA values. Multiple imputation (MI) will be applied to two measured variables: ADA binary response (positive/negative) and ADA continuous titer values. Multiple imputation will be done for each variable separately, then the two sets of imputed datasets will be merged in order to generate the imputed TEAR status. For subjects who are ADA negative at baseline, post-baseline missing values will be imputed using the binary response values obtained from logistic regression MI. Missing post-baseline values for subjects who are ADA positive at baseline will be derived from the continuous MI model. The primary efficacy analysis is based on the Week 24 (Visit 15) value. Subjects who discontinue treatment prematurely will be classified based on whether ADA values were obtained for the visits after treatment discontinuation (retrieved dropouts) or not.

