If the subject was ADA positive at baseline, then the imputed titer values will be used. The subject will be considered TEAR positive if the ADA titer at any post-baseline visit was $\geq 4\times$ the baseline titer. If none of the post-baseline titer values reached 4 times the baseline titer, then the subject will be classified as TEAR negative.

For each imputation, the proportion of responders, along with standard errors, will be estimated for each treatment group, and the estimate and standard error of the risk difference will be computed. These values will be combined across imputations using PROC MIANALYZE. Subsequently, the 90% confidence interval for the risk difference will be computed using the Wald confidence limit method.

An equivalence margin will be established as a function of the TEAR rate among the Novolog subjects. Under the null hypothesis of equivalence (i.e., $H_0: p_M = p_N$), the margin can be obtained as a function of the TEAR rate in the Novolog group using the following expression (Chow S-C et al., 2003, p. 91).

$$\delta = (z_\alpha + z_\beta) \sqrt{\frac{2p_N(1 - p_N)}{n_N}}$$

Selected values for δ are provided in Table 2 of Section 5 above. If the margin falls within the 90% confidence interval for the risk difference, then equivalence of MYL1601-D and Novolog will be declared.

These steps can be executed using code similar to the following:

```
proc freq data=simdata ;
title "90% Wald confidence interval";
by _imputation_;
ods output riskdiffcol2=rdiff1;
table group*resp / riskdiff (CL=WALD column=2) alpha=0.1;
weight count;
run;

data rdiff1; set rdiff1;
keep _imputation_ row risk ase lowercl uppercl;
if row='Difference';
run;

proc mianalyze data=rdiff1;
modeleffects risk;
stderr ase;
ods output ParameterEstimates=mirisk1;
run;

ods listing;
data parms1;
set mirisk1;
lowercl = estimate - (1.645*stderr);
uppercl = estimate + (1.645*stderr) ;
run;
proc print data=parms1;
var estimate stderr lowercl uppercl;
run;
```

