8.7.3.1 HbA1c

HbA1c is collected at week -7 to -4 (visit 1), baseline, week 12 (visit 11), and week 24 (visit 15). The measurements are performed by the central laboratory.

Actual values and changes from baseline at each time point will be computed and summarized by treatment group. Treatment difference and 95% confidence interval will be displayed along with p-values.

A sensitivity analysis for HbA1c will be performed using multiple imputation to impute missing values with non-missing subjects within the same treatment group using a pattern mixture model with the complete-case missing values (CCMV) method (Little 1993). After imputation, treatment difference, 95% CI, and p-values will be generated using same MMRM model as above. Sample imputation code is provided in Appendix 10.1.4.

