10.1.3 Combining the multiple imputation results to derive TEAR status

At this point there should be two sets of imputed data, each containing 30 records per subject, with all visits on the same record. These will need to be merged by subject and imputation. Then the TEAR values will be computed for each subject and analyzed. There are 3 steps:

1. Merge the imputed ADA binary response dataset with the imputed ADA titer dataset, by `usubjid avisitn _imputation_`. Then generate TEAR responder status based on the Week 24 (Visit 15) ADA values using the same algorithm as was used for the original data. This dataset will have one record per imputation per subject, but the TEAR values will be non-missing for all subject visits. Note that the variable TEAR may vary from imputation to imputation for the same subject. That is supposed to happen.
2. Run the primary efficacy analysis to create the 90% confidence interval using the Wald confidence limit method within each imputation. That will result in 30 confidence intervals, one for each imputation.
3. Combine the 30 confidence intervals to generate one summary confidence interval to be presented in the table.

Step 1.

Merge the imputed titer values by `usubjid avisitn _imputation_` to make a single dataset. Then create a new variable for TEAR status by following the ADaM specs for the definition of TEAR events, but using the new imputed ADA data. Again, the dataset will contain one record per imputation per subject, with a new response variable added to every record. For the purposes of the next steps below, this new response variable will be called TEAR.

- a. If the subject was ADA negative at baseline then do:
 - i. If any of RESP8–RESP15 is positive, then TEAR=1 for that imputation for that subject
 - ii. Else TEAR=0 for that imputation for that subject
- b. Else if subject was ADA positive at baseline then do:
 - i. If $ADA_x / ADA_0 \geq 4$ for any visit, where x is in 8–15, then TEAR = 1;
 - ii. else TEAR=0

Step 2.

Use code similar to what was used to analyze the primary efficacy endpoint, but run the code by `_imputation_`. For example,

```
/** step 2: Analyze the imputed datasets */  
proc freq data=imputed;  
by _imputation_;  
table trt*tear / alpha=0.10 riskdiff (cl= wald column=2)  
;  
output=outmi riskdiff;  
run;
```

Step 3.

Combine the 30 estimated statistics into one using PROC MIANALYZE.

```
proc mianalyze data=outmi;  
modeleffects _rdif1_ ;  
stderr e_rdif1;  

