ods output parameterestimates=parms;  
run;  
  
proc print data=parms;  
var estimate stderr lclmean uclmean probt;
```

```
run;
```

10.1.4 Multiple imputation for HbA1c.

HbA1c is measured at baseline and at Weeks 12 and 24 (visits 11 and 15). For purposes of these specifications, let HB_x represent the continuous value for HbA1c value at Visit x, where x takes the values 0 (for Baseline) or 11 or 15. The seed that will be used in the multiple imputation of ADA titer will be 24637883. The imputations will be combined using a mixed model for repeated measures.

There are 6 steps to this process:

1. Create a dataset with one record per subject, containing all values of HbA1c for all weeks (Baseline and Weeks 12 and 24 on one record); that is, each record would contain variables for HB₀, HB₁₁, and HB₁₅.
2. Run 30 Markov Chain Monte Carlo (MCMC) imputations to make the missing values in the dataset have a monotone missingness pattern. This will produce a dataset with an index variable `_imputation_` and otherwise the same variables as the input dataset. It will have one record per imputation per subject.
3. Run a pattern mixture model regression imputation on each imputed dataset from Step 2. This will generate a dataset with the same structure as the input dataset, but will have the missing values filled in.
4. Transform the dataset back into one record per subject per visit, with imputation number retained on each record.
5. Run a mixed model for repeated measures on the imputed datasets.
6. Combine the imputations to provide summary statistics.

Step 1.

The dataset for this imputation has to put the values for all weeks onto one record. That is, the dataset would have one record per subject, with 3 values for HB₀, HB₁₁, and HB₁₅.

One way this can be accomplished is the following:

```
data analysis (keep=usubjid trtp HB0 HB11 HB15);  
set indata;  
by usubjid avisitn;  
array y {3} HB0 HB11 HB15;  
retain HB0 HB11 HB15;  
if first.usubjid then do;  
    hb0 = base;  
    hb11 = .;  
    hb15 = .;  
end;
```

```
if avisit = 11 then hb11 = aval;  
if avisit = 15 then hb15 = aval;  
if last.usubjid then output;  
run;
```

Step 2.

```
/** step 2: Create monotone missingness using MCMC  
imputation */  
proc mi data=analysis seed=24637883 nimpute=1  
out=outdata1;  
mcmc impute=monotone;  
var hb0 hb11 hb15;  
run;
```

Step 3.

```
/** step 3: Perform PMM regression imputation */  
proc sort data=outdata1;  
run;  
  

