proc mi data=outdata1 seed=24637883 nimpute=30  
out=outdata2;  
by treatment;  
monotone reg(hb11 hb15 / details);  
mnar model (hb11 hb15 / modelobs=ccmv(k=1));  
var hb0 hb11 hb15;  
run;
```

Step 4.

Reverse the process from Step 1, creating one record per subject visit, retaining the imputation number on each record.

Step 5.

Use code similar to what was used to analyze the primary efficacy endpoint, but run the code by `_imputation_`. For example,

```
/** step 5: Analyze the imputed datasets */  
proc sort data=imputed;  
by _imputation_ subjid avisitn;  
run;  
  
proc mixed data=imputed;  
by _imputation_;
```

```
class trt avisitn dosetime site;
model chg = trt avisitn dosetime site trt*avisitn base /
ddfm=kr s;
repeated avisitn / type=un;
lsmeans trt*avisitn / diff cl;
ods output ConvergenceStatus=converge;
ods output diffs=trtdiff;
run;
```

Convergence status is assessed by the condition that:

```
if pdg=1 and pdh=1 and status=0
```

in the dataset converge above, then model has converged. In the above code, if the model does not converge, replace the type=un option by each of the following: type=toeph, type=toep, and type=cs. You will also need to replace ddfm=kr with ddfm=bw. Choose the best fit model by checking the AIC and selecting the model with the lowest one. Please contact the statistician if this step is necessary.

Step 6.

Combine the 30 estimated statistics into one using PROC MIANALYZE.

```
data trtdiff;
set trtdiff (where=(avisitn=_avisitn));
run;

proc sort data=trtdiff;
by avisitn _imputation_;
run;

[figure not shown]
proc mianalyze data=trtdiff;
by avisitn;
modeleffects estimate ;
stderr stderr;
ods output parameterestimates=parms;
run;

proc print data=parms;
var avisitn estimate stderr lclmean uclmean probt;
run;
```

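### SAP 8.7.2.1 and Appendix 10.1.3 give conflicting code for the pooled primary interval; used as printed, the appendix version would give 95% limits on the column-1 difference instead of the required 90% limits on TEAR-positive rates

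*SAP*

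**What the plan says.** SAP 8.7.1 fixes the level and direction of the primary interval: "The 90% confidence interval of the treatment difference (MYL-1601D minus NovoLog®) in the TEAR rate will be established" by the Wald method with multiple imputation. SAP 8.7.2.1 ties the decision to it: "The null will be rejected in favor of equivalence if the 90% confidence interval of the treatment difference is within the range" from −δ to δ. Table 2 carries the same level, with 0.05 under "Type I error 2 one-sided alpha" and 80% power.

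The code for the pooled interval appears twice.

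- **SAP 8.7.2.1.** PROC FREQ is run by imputation with `column=2` and `alpha=0.1`. The column-2 difference and its standard error go to PROC MIANALYZE, which has no level option. A data step then forms the limits by hand: "lowercl = estimate - (1.645*stderr" and the matching upper limit.
- **SAP Appendix 10.1.3, Steps 2 and 3.** The text again calls for a 90% Wald interval. `alpha=0.10` and `column=2` appear only on the PROC FREQ table statement. PROC MIANALYZE again has no level option, but it now receives the variables with suffix 1 ("modeleffects _rdif1" and the matching standard error). No data step follows, and the procedure's own limits are printed: "var estimate stderr lclmean uclmean probt".

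Appendix 10.1.4 ends in the same way for HbA1c, with no level option and "var avisitn estimate stderr lclmean uclmean probt". There the intended level is 95%. SAP 8.7.3.1 says: "After imputation, treatment difference, 95% CI, and p-values will be generated using same MMRM model as above".

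**The concern.** The primary conclusion depends on whether one interval lies inside the margin, so its level and its estimand must be the same wherever the SAP codes it. Section 8.7.2.1 refers the reader to Appendix 10.1 for the multiple-imputation code, and 10.1.3 describes its last step as producing the single interval for the results table. A programmer could reasonably work from the appendix.

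Two things differ there. The 90% level is lost at pooling, which costs power. The difference pooled is for column 1, which is TEAR-negative under the 0/1 coding in 10.1.3, so its sign is opposite to that of the 8.7.2.1 result. The direction matters for reporting because the SAP wants any TEAR difference read together with HbA1c, FPG, insulin dose, neutralizing antibodies and injection site reactions.

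**Working it through.** **Inputs.** n = 250 per arm, two one-sided tests at 0.05, 80% power and the margins come from SAP Table 2. The margin formula is in SAP 8.7.2.1. Its quantiles, z(0.95) and z(0.90), are those coded in Appendix 10.2. TEAR is coded 0/1 in Appendix 10.1.3.

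**1. Reproduce the plan's margins.** δ = (z(0.95) + z(0.90)) × √(2p(1−p)/250), with multiplier 1.645 + 1.282 = 2.926 before rounding.
- p = 5%: 2.926 × 1.949 = 5.70 points (Table 2: 5.7)
- p = 30%: 2.926 × 4.099 = 11.99 points (Table 2: 12.0)
- p = 50%: 2.926 × 4.472 = 13.09 points (Table 2: 13.1)

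All twelve rows agree within about 0.05 points. With z(0.80) in place of z(0.90), the 5% row would be 4.85, which does not match.

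**2. Reproduce the plan's power.** At zero true difference, power = 2Φ(δ/SE − z) − 1 and δ/SE = 2.926.
- 90% limits: 2Φ(2.926 − 1.645) − 1 = 0.800, as stated
- 95% limits: 2Φ(2.926 − 1.960) − 1 = 0.666

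The ratio of half-widths is 1.960/1.645 = 1.19. At a 30% reference rate the half-width rises from 6.74 to 8.03 points. The largest observed difference that still passes falls from 12.0 − 6.74 = 5.26 to 12.0 − 8.03 = 3.97 points.

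**3. Which level does 10.1.3 deliver?** The SAP's own usage points to 95%. The option-free call in 10.1.4 is meant to give 95% limits, and the same pattern cannot give 90% in 10.1.3. In 8.7.2.1 the level is also set on PROC FREQ, yet the 90% limits still have to be rebuilt after pooling. That rebuilding step is absent from 10.1.3.

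**4. Which difference?** In each arm the column-1 proportion is one minus the column-2 proportion. The column-1 difference is therefore exactly the negative of the column-2 difference for the same row order.

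**5. Worked example.** Take 86/250 = 34.4% on MYL-1601D and 75/250 = 30.0% on NovoLog®, with MYL-1601D as row 1. SE = √(0.344×0.656/250 + 0.300×0.700/250) = 4.17 points, and the margin is 11.99 points.

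| Code | Estimate | Interval | Inside ±11.99? |
|---|---|---|---|
| 8.7.2.1 (column 2, 90%) | +4.4 | −2.47 to 11.27 | Yes |
| Column 1, 90% (sign change only) | −4.4 | −11.27 to 2.47 | Yes |
| 10.1.3 as printed (column 1, 95%) | −4.4 | −12.58 to 3.78 | No |

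The change of level alters the decision. The change of sign alone does not.

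**The case against.** The strongest reply is that the SAP already specifies the right interval. Sections 8.7.1 and 8.7.2.1 and the text of 10.1.3 all say 90%, and the 8.7.2.1 code delivers it on column 2. The tipping-point code in 10.2 also uses column 2 and alpha 0.1. The appendix is headed as example code, and its Step 2 refers back to the primary analysis code. It also prints the estimate and standard error, which are the inputs to the 1.645 step, so it may simply be an abbreviated version. This stands as far as it goes: the method is not missing, and nothing shows that the appendix code would be run unaltered. It does not remove the contradiction between two printed versions.

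Three stronger readings are tempting but are not supported.

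- **A reader might infer a risk of a false equivalence claim.** The 95% interval contains the 90% interval from the same data, so anything that passes at 95% also passes at 90%.
- **A reader might infer that the reported MYL-1601D minus NovoLog® difference is reversed.** That depends on which arm is row 1. The coding of `trt` in 10.1.3 is not given. The treatment labels in 10.1.1 and 10.2 would put MYL-1601D first, but they belong to other variables. If NovoLog® is row 1, the column-1 difference already has the required direction.
- **A reader might object to 1.645 because it ignores degrees of freedom.** The t distribution with 498 degrees of freedom, close to the N − 2 rule in 8.7.2.1, changes the multiplier by under 0.3%. With 30 imputations and an assumed fraction of missing information of 0.1, 0.3 or 0.5, degrees of freedom of 29/λ² raise it by 0.02%, 0.28% or 0.80%, and power stays at 79.5% or more. This is negligible.

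**Conclusion.** The point holds as an internal contradiction in the code for the primary interval. If the 10.1.3 code were used as printed, the decision would rest on 95% limits: a half-width about 1.19 times larger, and power of about 67% against the planned 80%, a loss of about 13 points. The consequence is a possible failure where the plan's own rule would give a pass. The sign difference between the two codes is a reporting risk only.

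The power figures assume a normal approximation, zero true difference, 250 per arm and no between-imputation variance. The documents do not state PROC MIANALYZE's default level or the meaning of the suffix-1 variables. The first is inferred from the 95% use in 10.1.4 and the 1.645 step in 8.7.2.1, and the second is taken as column 1. Because 8.7.2.1 already contains workable code, this is a correction that should be made, not a defect in the planned method.

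**What to change.** Align Appendix 10.1.3 with 8.7.2.1:

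- Pool the column-2 risk difference and its standard error.
- State the coding of `trt` so that MYL-1601D is row 1 and the estimate is MYL-1601D minus NovoLog®.
- Obtain 90% limits at the pooling step, either with `alpha=0.10` in PROC MIANALYZE or with the 1.645 data step already in 8.7.2.1. Either is acceptable; choose one and state it in both places.

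The HbA1c code in 10.1.4 can stay, since 95% is intended there. The cost is a few lines of SAP code and text, with no change to data collection, sample size or the decision rule.

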8.7.3 Secondary endpoints

The following efficacy measures (both actual and change values) will be summarized at baseline and each scheduled visit.

- Change in HbA1c from baseline.
- Change in fasting plasma glucose from baseline.
- Change in prandial, basal insulin and total daily insulin dose per unit body weight (U/kg) from baseline.
- Change in 7-point self-monitored blood glucose (SMBG) profile from baseline.

A mixed model for repeated measures (MMRM) will be performed for continuous variables without imputing missing values. The MMRM model will include the fixed, categorical

effects of treatment group assignment, visit, treatment group-by-visit interaction, basal insulin dose time (AM/PM), and investigative site, as well as the baseline value as a continuous covariate.

The MMRM model results will be presented along with Least Squares (LS) means for the difference between the MYL1601-D and NovoLog[®] groups, standard errors, and two-sided 95% CIs for the difference between treatment groups. Contrasts of LS means at each scheduled visit will be used to evaluate all pairwise treatment comparisons, and 95% confidence intervals for treatment differences in LS means will be computed for each visit. The interaction of time points and treatment groups will also be presented. An unstructured covariance matrix will be assumed for within-subject error. The denominator degrees of freedom will be calculated according to the Kenward-Roger method.

In case of non-convergence of the above model using an unstructured covariance matrix, the following variance structures will be tested, and based on Akaike's information criteria the best fitting model will be chosen. The variance structures that will be considered for the within-subject variation in case of non-convergence are in this order: Heterogeneous Toeplitz, Toeplitz, and Compound Symmetry.

If convergence is still not obtained, the model may be revised to remove investigative site from the list of covariates.

All of the above analyses will be performed on the ITT set.

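### The example PROC MIXED code for the HbA1c imputation sensitivity analysis names no subject, contradicts the within-subject covariance in SAP 8.7.3, and cannot be fitted as printed

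*SAP*

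**What the plan says.** SAP 8.7.3 defines the repeated-measures model for the continuous secondary endpoints. On covariance it states: "An unstructured covariance matrix will be assumed for within-subject error". If that model does not converge, three simpler structures are tried and compared by AIC. The last resort is this: "If convergence is still not obtained, the model may be revised to remove investigative site from the list of covariates".

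SAP 8.7.3.1 adds a multiple-imputation sensitivity analysis for HbA1c: "After imputation, treatment difference, 95% CI, and p-values will be generated using same MMRM model as above". It points to Appendix 10.1.4 for sample code.

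In 10.1.4, Step 4 returns the imputed data to one record per patient and visit. Step 5 sorts by imputation, `subjid` and visit, then runs PROC MIXED separately for each imputation. The three statements that matter are:

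- CLASS: "class trt avisitn dosetime site"
- MODEL: "model chg = trt avisitn dosetime site trt*avisitn base"
- REPEATED: "repeated avisitn / type=un"

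There is no RANDOM statement. On non-convergence the programmer is told to "replace the type=un option by each of the following: type=toeph, type=toep, and type=cs", to change the degrees-of-freedom method from kr to bw, and to contact the statistician.

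**The concern.** The text promises a within-subject covariance, but the code never says what a subject is. The patient ID appears only in the sort, which has no effect on the model. PROC MIXED therefore has no way to tell which Week 12 and Week 24 values belong to the same patient.

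HbA1c comes first in the list of totality-of-evidence items that the SAP will use to interpret TEAR (SAP 2.1 and 8.7.1). If Step 5 is run as printed, its pre-specified sensitivity analysis produces nothing. The listed responses to non-convergence then send the programmer to the covariance structure, the degrees of freedom and possibly the site term, none of which is the cause.

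No correct template exists elsewhere in the SAP. This is its only PROC MIXED code. Step 5 tells the programmer to adapt the code for the primary endpoint, but that code (SAP 8.7.2.1) is a risk-difference table.

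**Working it through.** The documents give no figure for this model to reproduce, so the check is whether the coded covariance matrix can be inverted.

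**Inputs from the documents**

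- About 500 patients (SAP 5).
- Two post-baseline HbA1c visits, Weeks 12 and 24 (SAP 10.1.4), so 500 x 2 = 1000 records per imputation.
- Covariance structures un, toeph, toep and cs (SAP 10.1.4, Step 5).

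**Inputs assumed**

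- Without SUBJECT=, PROC MIXED treats all records in a BY group as one block. This is the standard rule of the procedure; the documents do not state it.
- For un and toeph: SDs 0.8 and 0.9, correlation 0.6. For toep and cs: variance 0.7, covariance 0.4. The documents give no HbA1c SDs or correlation. The rank result does not depend on these values.

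**1. Structure as coded.** Let G be the 2 x 2 covariance of the two visits. With one block indexed by visit, the covariance of records i and j is G[visit i, visit j]. In matrix form R = Z G Z', where Z is 1000 x 2 and marks each record's visit. Hence rank(R) ≤ 2.

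**2. Smallest case.** Take two patients and write G as variances a and b with covariance c. The rows of R are (a, c, a, c), (c, b, c, b), (a, c, a, c), (c, b, c, b). Rows 1 and 3 are identical, as are rows 2 and 4. The determinant is 0 and the rank is 2.

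**3. Planned size, built numerically**

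| Structure | Rank as printed | Rank with patient blocks | Smallest eigenvalue with patient blocks |
|---|---|---|---|
| un | 2 of 1000 | 1000 | 0.28 |
| toeph | 2 of 1000 | 1000 | 0.28 |
| toep | 2 of 1000 | 1000 | 0.30 |
| cs | 2 of 1000 | 1000 | 0.30 |

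As printed, the smallest eigenvalue is 0 to rounding under every structure. The rank stays at 2 for correlations of -0.9, -0.5, 0, 0.3 and 0.9.

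The eigenvalues with patient blocks can be checked by hand. For un, c = 0.6 x 0.8 x 0.9 = 0.432, the trace is 0.64 + 0.81 = 1.45, and the determinant is 0.5184 - 0.1866 = 0.3318. The smaller root is (1.45 - √(2.1025 - 1.3271))/2 = 0.28. For cs it is 0.7 - 0.4 = 0.30.

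**4. The fallbacks.** They change G, the degrees of freedom or the fixed effects. None changes Z, so the bound of 2 on the rank remains. With only two visits, toeph is the same model as un, and toep the same as cs, so the list offers little even in principle.

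**5. With a subject.** A REML fit with patient blocks and un converged on one simulated data set at the assumed values. It gave standard errors of 0.074 (Week 12) and 0.084 (Week 24) for the treatment difference. This shows only that the corrected model can be fitted.

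**The case against.** The best defence is that this is a slip in illustrative code, contradicted by clear governing text. The appendix is headed as example code, and Step 5 asks for something similar rather than identical. SAP 8.7.3 gives the within-subject structure, the model terms and the Kenward-Roger method. A programmer working from that text would add the subject. The SAP also checks convergence and sends any fallback to the statistician, who would be likely to see the cause. All of this stands, and it limits the weight of the point. It does not make the printed code right or reconcile it with the text.

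Three stronger readings are tempting, and the documents do not support them.

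- A reader might infer that HbA1c cannot be analysed under this SAP. But the sensitivity analysis takes its model from 8.7.3, not the reverse. The main HbA1c model has no code of its own and fails only if this block is reused.
- A reader might infer that a result with a simpler covariance, bw degrees of freedom or site removed would be reported. As printed, none of those variants gives an estimate either, so this code yields no wrong number.
- A reader might infer an inflated false-positive rate, by supposing that the repeated structure is deleted and the records treated as independent. No section permits that step, and 8.7.3 excludes it. The size and direction of any error would also rest on SDs that the documents do not give.

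**Conclusion.** The point holds for the code as printed. SAP 10.1.4, Step 5 conflicts with SAP 8.7.3. Followed literally, it gives a residual covariance matrix of rank 2 out of 1000 and no HbA1c treatment difference to combine across the 30 imputations. Neither the covariance fallbacks nor removal of site helps.

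The failure is visible, not silent. It concerns example code for one sensitivity analysis of one secondary endpoint. It reaches the main HbA1c, fasting glucose, insulin dose and SMBG models only through reuse of the code, and it does not touch the primary TEAR analysis. The conclusion rests on the standard single-block behaviour of PROC MIXED and on no assumed variance or correlation. It is a correction worth making, of modest weight.

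**What to change.** In SAP 10.1.4, Step 5:

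1. Choose one patient identifier and use it throughout. Step 1 keeps `usubjid`, while Step 5 sorts by `subjid`.
2. Add that identifier to CLASS, and add `subject=` with that identifier to the REPEATED statement beside `type=un`.
3. Keep `subject=` in the toeph, toep and cs fallbacks. State in one sentence that the fallbacks and removal of site apply only after the model with the subject identifier has failed to converge.
4. Use the same REPEATED statement wherever this code is reused for the 8.7.3 models.

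Two other details of the block need attention in the same edit if it is to run. The treatment variable is `trtp` in Step 1, `treatment` in Step 3 and `trt` in Step 5. The Step 1 KEEP list also omits the dose-time and site variables that Step 5 uses.

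The cost is a few lines of example code and one sentence in the SAP. It needs no protocol amendment or new data and does not affect the sample size.
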